During Period 1, a total of two protocol-allowed interventions are permissible. An intervention can occur on maximally two different lesions at the same visit or on the same lesion at two different study visits. The same lesion cannot be treated two times at the same visit. If a subject requires more than two interventions within the first 12 weeks, then they must discontinue taking study medication. However, these subjects will be requested to remain in the study and to complete all study procedures if possible.

During Period 2, maximally two interventions every 4 weeks are permitted. An intervention can occur on two different lesions at the same visit or on the same lesion at two different study visits. Within each 4-week period, the same type of intervention cannot be used two times on the same lesion. If a subject requires more than two interventions within a 4-week period or has two of the same interventions on the same lesion within that period, the subject must discontinue taking study medication. However, these subjects will be requested to remain in the study and to complete all study procedures if possible.

Analgesic Therapy: Subjects may receive non-opioid analgesics and also tramadol during the study. Any dose changes need to be recorded in the EDC. Oral and transdermal opioid analgesics (except for tramadol) for any reason are disallowed.

CYP3A4 Metabolism: Drugs that are strong inducers of the CYP3A4 enzyme, such as carbamazepine, phenobarbital, phenytoin, rifampin or St. John's wort are prohibited during the study because these drugs may substantially reduce the plasma concentrations of avacopan and reduce its effectiveness.

Substances that are strong inhibitors of CYP3A4, such as boceprevir, clarithromycin, conivaptan, indinavir, itraconazole, ketoconazole, lopinavir/ritonavir, mibefradil, nefazodone, nelfinavir, posaconazole, ritonavir, saquinavir, telaprevir, telithromycin, and voriconazole, and grapefruit juice should be avoided during the study, because these may modestly increase (~2-fold) the plasma concentrations of avacopan. However, these are not absolutely contra-indicated. If these must be used concomitantly with avacopan, subjects should be monitored carefully for any untoward side effects.

All concomitant medications taken during the course of the study must be recorded meticulously on the concomitant medication pages in the EDC.

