6.6. Study Week 12 (Day 85)

The Study Week 12 visit must occur within ± 2 days of the scheduled date. During this visit, the following study procedures will be performed:

- A physical examination including body weight;
- Vital signs (temperature, sitting blood pressure, heart rate) after at least 3 minutes of rest;
- Blood samples will be collected for serum chemistry, hematology, serum pregnancy test (in women of childbearing potential), and PK measurements; the date and time of collection of the PK sample will be recorded;
- Biomarker plasma sample will be collected;
- A 12-lead ECG will be taken to exclude any clinically significant findings;
- The date and time of the last dose of study drug prior to collection of the PK sample will be recorded;
- If the subject has not yet taken the morning dose of study drug for this day, the subject will be asked to take the dose;

- A urine sample will be collected for urinalysis;
- The anatomic location and number of HS inflammatory nodules, abscesses, fistulae, and hypertrophic scars will be recorded;
- Follow-up photography of lesions will be completed;
- Compliance with daily recording of pain in diaries will be checked and re-training provided, if necessary;
- Items for the Sartorius and modified Sartorius scores will be collected;
- IHS4 score will be calculated;
- The Investigator will complete the HS-PGA;
- Study personnel will record health-economic information;
- Subjects will be asked to complete the SF-36 v2, EQ-5D-5L, HiSQOL, DLQI, and WPAI:SHP forms;
- Drug accountability will be performed; the returned bottles of study drug will be checked to make sure the subject is taking the study drug as instructed;
- Study drug will be dispensed. Note: At this visit, subjects who were assigned to placebo arm will be re-randomized to receive 10 mg or 30 mg avacopan twice a day;
- Any changes in concomitant medication use will be recorded, including alcohol intake, recreational drug use, non-prescription medications, herbal preparations or special diets;
- Any adverse events will be recorded;
- After all study procedures have been completed, the subject will be reminded to:
 - Record severity of skin pain and study drug dosing in daily diary;
 - Come to the study center for the Week 16 study visit;
 - Store the study drug in a cool and dry place according to label instructions for the duration of the study;

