7.2. Safety Assessments

7.2.1. Physical Examinations and Vital Signs

A physical examination (including evaluation of general appearance/mental status, head, eyes, ears, nose, throat, and the following body systems: dermatologic, cardiovascular, respiratory, gastrointestinal, musculoskeletal and neurologic) will be performed at visits indicated in the [Time and Events Table](#). Findings must be recorded in the source documents.

Any new or worsening findings upon physical examination need to be recorded as adverse events.

Body weight will be measured as part of the physical examinations. Height needs to be recorded only at Screening. BMI will be calculated in the EDC from the body weight and height measurements.

Vital signs and 12-Lead ECG will be measured during Screening and on each scheduled study day as indicated in the [Time and Events Table](#). Sitting blood pressure, pulse rate, and body temperature will be measured. All vital signs assessments will be performed after the subject has rested for at least three minutes.

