For the analysis of time to loss of response (LOR), the treatment difference between the avacopan 30 mg vs. placebo to avacopan 30 mg, avacopan 10 mg vs. placebo to avacopan 10 mg, avacopan 30 mg group vs. avacopan 10 mg group, and placebo to avacopan 30 mg vs. placebo to avacopan 10 mg will be analyzed using the stratified log-rank test with the baseline Hurley Stage (Stage II vs. III), concomitant antibiotic therapy with allowed antibiotics (Yes vs. No), and anti-TNF drug use (Treatment naïve vs. Previous treatment) as the stratification variables. Subjects without LOR or lost follow-up will be censored at the date of the last assessment of number of HS lesions. Kaplan-Meier curves will be provided by treatment group.

IX. Safety Analyses

Safety analyses will be performed in the Safety Analysis Set using the actual treatment group.

A. Adverse Events

All subjects will be assessed regularly for potential occurrence of adverse events (AEs) throughout the study until the subject is off study. The Medical Dictionary for Regulatory Activities (MedDRA; Version 21.1) will be used to code all adverse events to a System Organ Class (SOC) and Preferred Term (PT).

A treatment-emergent AE (TEAE) in Period 1 is defined as any AE that occurs after the first dose of study treatment in Period 1 and before the date of first dose of study treatment in Period 2.

A treatment-emergent AE (TEAE) in Period 2 is defined as any AE that occurs after the first dose of study treatment in Period 2.

A treatment-emergent AE (TEAE) for all avacopan, is defined as any AE that occurs after the first dose of avacopan treatment in study.

The incidence of TEAEs will be summarized and tabulated by treatment group and period.

The severity of each AE will be assessed as mild, moderate, severe, lifethreatening, fatal, or death. Several occurrences of the same AE in one subject will be counted once and the one with maximum severity will be counted.

The relationship of each AE to the blind study medication will be classified as probably not related or possibly related. Several occurrences of the same AE in one subject will be counted once and the one with the maximum relationship to blind study medication will be counted. If an AE is missing the relationship to blind study medication, the event will be assumed to be probably related for analysis and summarization.

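### The SAP's Period 1 TEAE window closes badly: pre-dose events on the Week 12 switch date fall in neither period, and subjects with no Period 2 dose have no closing date

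*SAP*

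**What the plan says.** SAP section IX.A opens the Period 1 TEAE window once Period 1 dosing has begun and requires the event to fall "before the date of first dose of study treatment in Period 2". For Period 2 it counts "any AE that occurs after the first dose of study treatment in Period 2". The first boundary is a calendar date and the second is a dose. No other end is given for Period 1, such as a visit, a study day or a lag after last dose. The same section says adverse events are assessed "throughout the study until the subject is off study".

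The switch happens at Week 12. Protocol 6.6 reads: "Study drug will be dispensed. Note: At this visit, subjects who were assigned to placebo arm will be re-randomized". That visit also has chemistry, hematology and a physical examination, and its ECG is the only one in Period 1 after baseline ("A 12-lead ECG will be taken to exclude any clinically significant findings"). Protocol 7.2.1 adds: "Any new or worsening findings upon physical examination need to be recorded as adverse events".

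Stopping drug does not end follow-up. Protocol 4.4 asks sites to keep following subjects who stop. Protocol 5.7 requires drug to stop after more than two lesion interventions in the first 12 weeks, yet says "these subjects will be requested to remain in the study and to complete all study procedures if possible".

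**The concern.** Safety against placebo, judged partly by adverse event incidence, is a primary objective, and Period 1 is the only placebo-controlled part of the study. Its TEAE tables need a window that is complete and of the same nominal length for everyone.

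The text fails in two ways, both at the closing end. For subjects who enter Period 2, mixing a date with a dose leaves a gap on the switch date, which on the planned schedule is a visit with many assessments. For subjects who never take Period 2 drug, the only closing event does not exist. They belong to the Period 1 safety population but not to the Period 2 one, which needs a Period 2 avacopan dose (SAP VI.J). By period, their later events can therefore fall only in the Period 1 tables. One route into this group is repeated lesion intervention, which is itself an adverse event of special interest.

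**Working it through.** **Where the boundary falls.** Inputs are the visit days in the protocol's Time and Events Table and the Period 2 target days in SAP Table 1. Implied day of first Period 2 dose = protocol day − target day + 1.

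- Week 16: 113 − 29 + 1 = 85
- Week 20: 141 − 57 + 1 = 85
- Week 24: 169 − 85 + 1 = 85
- Week 28: 197 − 113 + 1 = 85
- Week 32: 225 − 141 + 1 = 85
- Week 36: 253 − 169 + 1 = 85

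This agrees with 84 days of Period 1 treatment (Protocol 3.3). The Week 44 target in Table 1 (197) is out of line, since it implies Day 113. Table 3 gives 225, which again implies Day 85.

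**An event dated Day 85 when the first Period 2 dose is also on Day 85.**

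| Onset | Before the dose date? | After the dose? | Result |
|---|---|---|---|
| Before the dose | No | No | Neither period |
| After the dose | No | Yes | Period 2, correctly |
| Time not recorded | No | Unknown | No rule |

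The start-date imputation in SAP VI.C refers only to the first study dose, so it does not help. Table 1, by contrast, keeps assessments in Week 12 through the Period 2 randomization day. A Week 12 laboratory value can thus be Period 1 data while the event it generates is not a Period 1 TEAE. The gap covers at most 1 of 85 days (1.2%).

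**No Period 2 dose.** Week 44 is Day 309. Extra days counted = 309 − 84 = 225 at most; 309 / 84 = 3.7 times the planned window.

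The documents do not say how many subjects will stop in Period 1 and stay on study. Let *s* be that share of an arm of 130. Planned Period 1 person-days are 130 × 84 = 10,920. Extra person-days are at most 130 × *s* × 225.

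| Assumed *s* | Extra person-days | Relative to plan |
|---|---|---|
| 2% | 585 | +5.4% |
| 3.5% | 1,024 | +9.4% |
| 7% | 2,048 | +18.8% |
| 10% | 2,925 | +26.8% |

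The 7% row borrows the plan's attrition figure as a scale only. That figure covers the whole trial and includes subjects who leave the study. All rows are upper bounds, because they assume follow-up to Week 44.

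**Effect on incidence (illustration).** Assume a constant hazard, unchanged off drug. Then p309 = 1 − (1 − p84)^(309/84), and the tabulated arm incidence is (1 − *s*) × p84 + *s* × p309.

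| True 12-week incidence | p309 | Tabulated, *s* = 3.5% | Tabulated, *s* = 7% |
|---|---|---|---|
| 5% | 17.2% | 5.4% | 5.9% |
| 30% | 73.1% | 31.5% | 33.0% |
| 50% | 92.2% | 51.5% | 53.0% |

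**Effect on the difference between arms.** With equal true incidence, the distortion is (difference in *s*) × (p309 − p84). It is zero if *s* is equal. A 5-point difference in *s*, again an assumption, gives 0.05 × 42.2 = 2.1 points for a 50% event and 0.05 × 12.2 = 0.6 points for a 5% event. The sign is that of the difference in *s*. For scale, the standard error of a difference, √(2p(1 − p)/130), is 6.2 and 2.7 points.

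**The case against.** The strongest reply is that other text already bounds Period 1. SAP section II describes it as running from Day 1 to Week 12, IX.A tabulates TEAEs by SOC and PT by treatment received in the period of onset, and VIII.A limits the primary analysis to Period 1 data. This shows intent, but it does not override the explicit TEAE definition. Nor does it say what becomes of a late event in a subject with no Period 2 dose. The Day 114 cap in Tables 1 and 3 governs assessment visits, not adverse events.

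A second reply is that the same-day gap is conditional. Protocol 6.6 has the morning dose taken at the visit if still due, without naming the kit, and SAP VII.C takes the actual Period 2 start from the drug accountability form. If that date is later, Week 12 events stay in Period 1. This stands, and it limits the gap to pre-dose or untimed onsets on a shared date.

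Third, a reader might infer that end-of-period laboratory and ECG findings are lost. They are not. Laboratory values are summarised by visit, with grade and shift tables for key parameters; abnormal ECGs are listed by visit; and there is a listing of all adverse events. What is affected is TEAE and AESI allocation.

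Fourth, a reader might infer that the open window hides an avacopan excess, because lesion-driven stopping could be commoner on placebo. The documents do not support a direction. Protocol 4.4 also requires drug to be paused or stopped for laboratory abnormalities, and if those were commoner on avacopan the bias would reverse.

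**Conclusion.** Both defects follow from the SAP's own text. The same-day gap is small: at most about 1 day in 85, arising only when the first Period 2 dose falls on the visit date and the onset is pre-dose or untimed. The missing closing date matters more. Each affected subject can contribute up to 225 extra days, so 12-week incidence is overstated in any arm that has such subjects with later events.

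It would go too far to say that the opening edge is also at fault, or that the placebo comparison is shown to be wrong. One rule applies to all three arms, and the comparison is biased only if stopping or later follow-up differs between them. Neither size nor direction can be fixed from the documents. The incidence figures above rest on assumed shares, a constant hazard and complete follow-up to Week 44. The case for change is that a primary safety objective should not depend on an undefined boundary.

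**What to change.** In SAP IX.A:

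- Use one shared boundary. Period 1 TEAEs have onset from the first Period 1 dose up to the first Period 2 dose; Period 2 TEAEs have onset from that dose onward.
- Assign events found at the pre-dose Week 12 assessments to Period 1. State one rule for other untimed onsets on the switch date, applied identically in all arms.
- For subjects with no Period 2 dose, close Period 1 at the Week 12 visit date. If that visit is missed, close it at Day 87, the end of the protocol's visit window (Day 85 + 2). Report later events in a separate off-treatment table.

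The cost is SAP wording, a programming rule and one extra table. No new data are needed.

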8.4.1 Modified Intent-to-Treat Population

For the purposes of efficacy data analysis, the Modified Intent-to-Treat (mITT) population will be used. This population will include all subjects who are randomized and received at least one dose of study drug. The efficacy population will be analyzed according to the treatment group each subject is randomized to. The mITT population will be the primary analysis population for the efficacy analysis.

The mITT populations are defined for the two treatment periods as the following:

- The mITT1 Population in Period 1 is defined as all subjects who are randomized at baseline and have received at least one dose of study drug during Period 1.
- The mITT2 Population in Period 2 is defined as all subjects who have received at least one dose of study drug during Period 2.

8.4.2 Per-Protocol Population

The Per-Protocol (PP) population will consist of all randomized subjects who receive at least one dose of study drug and do not have protocol deviations that could significantly affect the interpretation of the results for the primary endpoints. Subjects' inclusion/exclusion from the PP population will be determined and documented prior to the database lock and unblinding.

8.4.3 Safety Population

randomized and have received at least one dose of study drug, and who are not from study Site 138. Subjects from Site 138 will be excluded from the ITT Population due to potential misconduct and non-compliance at site 138.

The ITT populations are defined for the two treatment periods as the following:

- The ITT1 Population in Period 1 is defined as all subjects who are randomized at baseline and have received at least one dose of study drug during Period 1.
- The ITT2 Population in Period 2 is defined as all subjects who have received at least one dose of study drug during Period 2.

Per Protocol Population

The per protocol (PP) population for period 1 will consist of ITT1 and do not have protocol deviations that could significantly affect the interpretation of the results for the primary endpoints. Subjects' inclusion/exclusion from the PP population will be determined and documented prior to the database lock and unblinding.

Per-Protocol Population in Period 1 (PP1) will include subjects in ITT1 who meet all the following criteria:

- Receive at least 70% of the planned study drug in Period 1 for subjects who complete Period 1 or receive at least one dose of study drug and discontinue Period 1
- Provide at least one post
 Baseline assessment on lesion count
- Meet the Hurly stage II: Total SCAR and Fistula counts > 0 at either screening or Day 1.
- Have Baseline AN count ≥ 3
- Have Baseline draining fistula count ≤ 20

The Safety Populations are defined as the following:

- The Safety Population in Period 1 is defined as all subjects who are randomized at baseline and have received at least one dose of study drug during Period 1.
- The Safety Population in Period 2 is defined as all subjects who received at least one dose of avacopan during Period
- The All Avacopan
 Treated Population is
 defined as all subjects
 who receive at least one
 dose of avacopan in any
 treatment period.

The Safety Populations will be analyzed according to the assigned treatment group. In the event that a subject receives a treatment regimen that does not correspond to the assigned treatment, the subject will be included in the analysis group of the treatment actually received.

- Do not take the following exclusionary medications during the exclusionary screening period or during Period 1:
- Any concomitant antibiotics for the treatment of HS (except the protocol allowed rescue medication which will result in counting the subjects as non-responders, or having the last observation prior to the use of these treatments carried forward).
- Anti-TNF-a (Humira),
 Methotrexate (MTX), cyclosporin,
 corticosteroids, and retinoids for any
 reason, or other medication for
 treatment of their HS that will
 confound the efficacy evaluation (to be
 determined and documented in the
 classification results prior to blind
 break).

Per-Protocol Population in Period 2 (PP2) will be defined separately.

Subjects included in the Per-Protocol Population will be analyzed as treated. That is, if a subject receives the treatment that is not the randomized assignment during their entire participation of a period, the subject will be analyzed according to the treatment that the subject actually received in the period.

Safety Population

The Safety Population will include all subjects who are randomized and have received at least one dose of study drug, excluding those subjects who are from study Site 138. Due to the reasons stated above safety data of subjects from site 138, including adverse events, will be listed separately only and not be included in the summary tables:

 The Safety Population in Period 1 (Safety1) is defined as all subjects who are randomized at

		baseline and have received at least one dose of study drug during Period 1. The Safety Population in Period 2 (Safety2) is defined as all subjects who received at least one dose of avacopan during Period 2. The All Avacopan Treated Population is defined as all subjects who receive at least one dose of avacopan in any treatment period. The Safety Populations will be analyzed according to the assigned treatment group. In the event that a subject receives a treatment regimen that does not correspond to the assigned treatment consistently, the subject will be included in the analysis group of the treatment actually received.
Adding Ranked Secondary Endpoints	 Page 69: Secondary Efficacy Endpoints Secondary efficacy endpoints include: 1. Reduction of IHS4 score relative to baseline at Week 12; 2. Proportion of subjects achieving at least 30% reduction and at least 1 unit reduction from Day 1 in the subject's global assessment of skin pain (NRS30) in subjects with a baseline NRS of at least 3, evaluated at Week 12; weekly averages of daily pain will be calculated based on subjects' daily diary recording of the worst pain experienced in the previous 24 hours; 3. Change from Day 1 to Week 12 in the modified Sartorius score to quantify the severity change of HS; 	The following secondary efficacy endpoints will be analyzed according to the rank order as the follows: 1. Change from Baseline in total AN count at Week 12; 2. Proportion of subjects achieving at least 30% reduction and at least 1 unit reduction from Baseline in the subject's global assessment of skin pain (NRS30) in subjects with a Baseline NRS of at least 3, evaluated at Week 12; weekly averages of daily pain will be calculated based on subjects' daily diary recording of the worst pain experienced in the previous 24 hours; 3. Proportion of subjects with baseline Hurley Stage II who achieved an abscess and

	Proportion of subjects with baseline Hurley Stage II who achieved an abscess and	inflammatory nodule count of 0, 1, or 2 at Week 12;
	inflammatory nodule count of 0, 1, or 2 at Week 12.	Reduction of IHS4 score relative to baseline at Week 12;
		 Change from Baseline in inflammatory nodule count at Week 12;
		 Change from Baseline in abscess count at Week 12;
		Change from Baseline in draining fistula count at Week 12;
		Change from Baseline to Week 12 in the modified Sartorius score to quantify the severity change of HS.
Added other efficacy endpoints	Page 69 Other Efficacy Endpoints	Other Efficacy Endpoints
	The following efficacy endpoints will be analyzed from Day 1 to each timepoint up to Week 44, where applicable:	The following efficacy endpoints will be analyzed from Baseline to each timepoint up to Week 44, where applicable:
	 Proportion of subjects achieving HiSCR; Proportion of subjects achieving at least 30% reduction and at least 1 unit reduction from Day 1 in subject's global assessment of skin pain (NRS30), in subjects with a Day 1 NRS of at least 3; 	 Proportion of subjects achieving HiSCR, HiSCR₇₅, and HiSCR₉₀;
		Proportion of subjects achieving at least 30% reduction and at least 1 unit reduction from Baseline in the subject's global
	Proportion of subjects with baseline Hurley Stage II who achieved an abscess and inflammatory nodule count of 0,	assessment of skin pain (NRS30), in subjects with a Baseline NRS of at least 3; 3. Proportion of subjects with
	1, or 2; Change from Day 1 in inflammatory nodule count, abscess count, draining fistula	baseline Hurley Stage II who achieved an abscess and inflammatory nodule count of 0, 1, or 2;
	count, and total AN count;	Change from Baseline in inflammatory nodule count,

- Change from Day 1 in the Sartorius score, modified Sartorius score, IHS4 score, and HS-PGA to quantify the severity change of HS;
- Change from Day 1 in patientreported outcomes: SF-36 v2, EQ-5D-5L, HiSQOL, and DLQI;
- Proportion of subjects who
 experienced flare, defined as an at
 least 25% increase in AN counts
 with a minimum increase of 2 AN
 lesions relative to Day 1;
- Duration of flare in days
 (calculated from the day when
 flare is observed to the day prior
 to the observation that flare is no
 longer present; of note, there
 could be multiple periods that
 flares are observed, in which case,
 the total days from the multiple
 periods will be used);
- Proportion of subjects who experience at least 25% increase in draining fistula counts with a minimum increase of 2 draining fistula counts relative to Day 1;
- During Period 2, Proportion of subjects with a loss of response (LOR), defined as loss of at least 50% of AN count improvement achieved from Day 1 to Week 12;
- Time to LOR during Period 2;
- Proportion of subjects who received oral antibiotic rescue therapy;
- Proportion of subjects who start disallowed opioid pain therapy;
- Proportion of subjects who undergo lesion intervention due to HS;

- abscess count, noninflammatory count, draining fistula, non-draining fistula, total fistula count, and total AN count;
- % Change from Baseline in inflammatory nodule count, abscess count, noninflammatory count, draining fistula, non-draining fistula, total fistula count, and total AN count among subjects who have at least one corresponding lesion at Baseline.
- Change from Baseline in the Sartorius score, modified Sartorius score, IHS4 score, and HS-PGA to quantify the severity change of HS;
- Change from Baseline in subject-reported outcomes: SF-36 v2, EQ-5D-5L, HiSQOL and DLQI;
- Proportion of subjects who experienced flare, defined by at least a 25% increase in AN counts with a minimum increase of 2 AN lesions relative to Baseline;
- Duration of flare in days
 (calculated from the day
 when flare is observed to the
 day prior to the observation
 that flare is no longer present;
 of note, there could be
 multiple periods that flares
 are observed, in which case,
 the total days from the
 multiple periods will be
 used);
- Proportion of subjects who experience at least 25%

- Number of lesion interventions due to HS;
- 16. Health-economic information:
 - a. WPAI:SHP: Change from Day 1 to each timepoint during Period 1 and Change from Week 12 to each timepoint during Period 2 and including the follow-up period;
 - Hospitalizations
 (cumulative): Number of
 Hospitalizations total and
 due to HS, Number of days
 hospitalized, Number of
 days missed from work;
 - Emergency or Urgent Care visits (cumulative): Number of visits total and due to HS, Number of days (or hours where applicable) missed from work;
 - d. Lesion interventions for HS (cumulative): Number of days (or hours where applicable) missed from work due to HS lesion interventions.

- increase in draining fistula counts with a minimum increase of 2 draining fistula counts relative to Baseline;
- During Period 2, proportion of subjects with a loss of response, (LOR) defined as loss of at least 50% of AN count improvement achieved from Week 12 in Period 1;
- 12. Time to LOR during Period 2;
- Proportion of subjects who received oral antibiotic rescue therapy during Period 1 and Period 2 including the followup period separately;
- Proportion of subjects who start disallowed opioid pain therapy during Period 1 and Period 2 including the followup period separately;
- Proportion of subjects who undergo lesion intervention due to HS during Period 1 and Period 2 including the follow-up period separately;
- Number of lesion interventions due to HS during Period 1 and Period 2 including the follow-up period separately;
- 17. Health-economic information:
 - WPAI:SHP: Change from Baseline to each timepoint during Period 1 and Change from Week 12 to each timepoint during Period 2 and including the follow-up period;
 - Hospitalizations
 (cumulative): Number
 of Hospitalizations
 total and due to HS,
 Number of days

		4 2 4 4 5 7 4
		hospitalized, Number of days missed from work during Period 1 and Period 2 including the follow-up period separately;
		c. Emergency or Urgent Care visits
		(cumulative): Number
		of visits total and due
		to HS, Number of days
		(or hours where
		applicable) missed
		from work during
		Period 1 and Period 2
		including the follow-up
		period separately;
		d. Lesion interventions
		for HS: Number of
		days (or hours where applicable) missed
		from work due to HS
		lesion interventions
		during Period 1 and
		Period 2 including the
		follow-up period
		separately.
Updated the definition	Page 71:	Lesions that received intervention
of non-responders	The following are examples for subjects who will be counted as non-	(incision and drainage, or intralesional
	responder:	injection of corticosteroid) will be
	 Concomitant anti-TNF-α treatment or 	counted as permanently present from
other treatments with clinically relevant impact on HS; • Antibiotic rescue therapy; • Non-protocol specified lesion intervention, or higher than permitted frequency or number of pre-specified lesion interventions. Protocol-specified		the date of the intervention.
	In order to adjust for the impact of	
		major protocol disallowed treatments
		on the results of the trial, efficacy assessments obtained after the start of
	major protocol disallowed treatments	
	lesion interventions will not be counted as Non-responder.	will be excluded from the analysis.
	counted as 14011-1esponder.	Subject will be counted as non- responders for the categorical
		variables and have their last
		observation carried forward for
		continuous variables.

[·	1 =		
Missing data	Page 71:	Added MI method for	
imputation method has	Missing Data Analysis: For missing	selected binary secondary	
been updated	data analysis, the following imputation	efficacy endpoints.	
	rules will be applied to categorical and	Added ANCOVA model for	
	continuous efficacy variables,	selected binary secondary	
	respectively:	efficacy endpoints.	
	Categorical Efficacy Variables: NRI		
	will be the primary approach for categorical variables. The NRI analysis		
	will count subjects who have missing		
	values at a specific visit as non-		
	responders for that visit. LOCF will be		
	the secondary approach for the missing		
	data analysis.		
	Continuous Efficacy Variables:		
	LOCF will be the primary approach		
	for continuous efficacy variables of		
	missing data. The LOCF analyses will		
	have their valid efficacy assessments		
	from the previous visits to impute		
	missing data at later visits. Baseline		
	efficacy evaluations will not be carried		
	forward.		
A 44 A OTTO A T	D 22	A CTICATE	
Added CTCAE grades	Page 73:	Added analyses by CTCAE grades.	
for lab parameters	No CTCAE was mentioned in the		
	protocol.		
Added more subgroup	Page 75:	The subgroups are defined as follows:	
analyses.	The analysis of the efficacy endpoints	Randomization stratification	
	may be adjusted by the following	variables	
	variables in the form of covariate	- Hurley Stage (II, III)	
	analysis, stratified analysis, and/or	- Concomitant	
	subgroup analysis:		
	Randomization stratification	antibiotic therapy	
	variables	(Yes, No)	
	- Hurley Stage II vs. Hurley Stage III	- Anti-TNF-α	
	- Concomitant antibiotic therapy (Yes vs. No)	treatment (Treatment	
	- Anti-TNF-α treatment (Treatment	naïve, Previous	
	naïve vs. Previous treatment)	treatment)	
	• Sex	Sex (Male, Female)	
	• BMI	BMI category: Normal (< 25)	
	Baseline weight	kg/m^2), Overweight (25 – <	
	Age at diagnosis of HS	30 kg/m^2), obese (30 – < 40	
	Age at study entry	kg/m²), Morbid obesity (≥ 40	
	Duration of HS	kg/m²)	
	Subject's age, race, and ethnicity	Age at diagnosis of HS (<	
	Baseline inflammatory nodule count	median, ≥ median)	
	Baseline abscess count	Age at study entry (<65 years Sections)	
I	 Baseline draining fistula count 	vs. ≥ 65 years)	
	_		
	Baseline Sartorius and modified	 Duration of HS (< median, ≥ 	
	_		

 Baseline AN count (< 5, 5- 10, >10)
 Baseline inflammatory
nodule count (< median, ≥
median)
Baseline abscess count (<
median, ≥ median)
 Baseline draining fistula
count (< median, ≥ median)
 Baseline modified Sartorius
score (< median, ≥ median)
 Previous systemic HS
treatment (includes TNF
inhibitor use but excludes
antibiotic use)
 Geographic distribution
(Northeastern Region,
Southeastern Region,
Western Region, Midwestern
Region, and Southwestern
Region)
region/

Sponsor Approval Form

Project:	BZA52227	Sponsor:	ChemoCentryx, Inc.
Date:	10/07/2020	Protocol:	CL016_168
Item(s) Sub	mitted for Approval	File	name (for electronic documents)
	Configuration		
	nd Roles		
	esign – PDF of forms	AND	
	eck Specifications		
	mpletion Guidelines		
	onciliation Guidelines		
☐ Coding R			
	ation Schedule Specification		
	ation Plan		
☐ Unblindin			
	a Transfer Requirements		
	ecifications		
SDTM Tra			
☐ CDF Spec			
☐ CDF Test			
☐ Site Paym	nent Criteria Specifications		
Statistical	Analysis Plan – text	1	lients\ChemoCentryx\BZA52227\Bios\Statistical Analysis \Drafts\v7.0\CCX_168 SAP 07OCT2020
☐ Statistical	Analysis Plan -		*
data display	shells		
